## Administrative information

**1) Title:** A multicentre, analyst-blinded, randomised, superiority study to compare the efficacy of Video Observed Treatment (VOT) versus Directly Observed Treatment (DOT) in supporting adherence in patients with active tuberculosis.

**2a) Trial identifier and registry name:** ISRCTN26184967

**2b) All items from trial registration dataset**

**3) Protocol Version:** V3 - 28/07V2 - 14/05/2014

**4) Funding:** National Institute of Health Research (NIHR) Programme Grant

## **5c) Role of Study Sponsor and Funders**

The study sponsor has responsibility for the overall conduct and quality of the trial. The funder influenced study design through the peer review process but otherwise the funder and sponsor had and will have no role in the collection, management, analysis, and interpretation of data; writing of the report; and the decision to submit the report for publication.

## **5d) Additional roles and responsibilities.**

Principal investigator (PI)

- Design and conduct of TB Reach VOT trial
- Preparation of protocol and revisions
- Preparation of investigators brochure (IB) and CRFs [case report forms]
- Organising steering committee meetings
- Publication of study reports
- Determining members of TMC [Trial Management Committee]

Steering committee (SC)

- (see section 5a for members) plus Study co-ordinator ([name])
- Agreement of final protocol
- Liaising with study sites
- Arranging site quality control visits
- Reviewing progress of study and if necessary agreeing changes to the protocol and/or investigators brochure to facilitate the smooth running of the study.
- Budget administration and contractual issues with individual centres

External Trials Management Committee (TMC)

- Chair – [name] –UCL MRC Clinical Trials Unit
- Members – [name], Consultant in Respiratory and General Medicine, Central Manchester University Hospitals, [name], Consultant in Infectious Diseases – Monklands Hospital, Airdrie, Scotland, [name] – Lay Representative
- Advising on study design
- External scrutiny of study procedures, implementation and recruitment

- Review of SUSAR [Serious unexpected suspected adverse events]

#### Data monitoring Committee

The study is a non-pharmaceutical intervention with no planned stopping rules or interim analyses. There will therefore be no formal data monitoring committee. However the trial statistician ([name]) will prepare data reports for the TMC to be checked by an independent statistician from MRC CTU.

#### Data manager

- Maintenance of trial IT system and data entry
- Data verification
- Responsible for trial master file

#### Lead investigators

In each participating centre a lead investigator (senior nurse or clinician) will be identified, to be responsible for identification, recruitment, data collection and completion of CRFs, along with follow up of study patients and adherence to study protocol and investigators brochure.

## Introduction

### 6a & b) Background

In the United Kingdom, tuberculosis patients at high risk of poor adherence to tuberculosis treatment are recommended to have directly observed treatment (DOT) to minimise the risk of relapse, drug resistance and spread of infection. Groups eligible for DOT include patients with social risk factors (including alcohol or drug use, history of imprisonment, homelessness), mental health problems, evidence of poor adherence, previous TB treatment and clinically complex disease requiring extra support. Direct observation can be time and resource intensive for both patients and NHS services, requiring at least three visits per week. The three times weekly regime used for DOT may also be less satisfactory than a daily regime. In the UK, surveillance data suggest that a high proportion of patients who are recommended for DOT do not receive DOT. In the US DOT is the recommended mode of treatment for all TB patients. Recently the University of California San Diego (UCSD) has developed a smart phone “app” allowing patients to easily submit video recordings of themselves taking treatment to a secure server for reading by a health care worker (Video Observed Treatment – VOT). This has been shown to be feasible and highly acceptable in

non-socially complex cases in the US but has not been trialled in more socially complex patients such as those recommended for DOT in the UK. Our study team have pioneered the use of VOT with the pan London Find&Treat TB outreach service (but without the use of a dedicated smart phone app) in socially complex cases in London and again found it to be highly acceptable to patients. We have also modelled potential cost savings through using DOT rather than VOT and found VOT to be considerably cheaper to deliver than DOT. We are collaborating with UCSD to use their VOT “app” in a trial of effectiveness in UK patients eligible for DOT.

**7) Research Hypothesis:** In comparison to DOT, VOT increases the proportion of patients who have more than 80% of doses observed during a 2 months period.

**Primary Objective:** To assess the effectiveness of VOT in comparison to DOT on adherence to treatment

**Additional Objectives**

- To measure the impact on adherence over 6 months
- To measure impact on loss to follow up and treatment completion
- To measure effect on culture conversion and development of resistance
- To measure impact on transmission
- To measure impact on quality of life and patient satisfaction
- To assess cost effectiveness of VOT

**8) Description of trial design.**

The TB Reach VOT trial is designed as a randomised, controlled, analyst blinded multicenter superiority trial with two parallel groups (VOT and DOT) with a 1:1 allocation and a primary endpoint of 80% of doses being observed over a 2 month period.

## **Methods: Participants, interventions, and outcomes**

**9) Description of study settings:** Tuberculosis outpatient clinics in London and Birmingham and the London TB outreach service: Find&Treat.

**10) Inclusion criteria:** Any patient 16 years of age or older eligible for DOT at participating clinics regardless of whether the patients have previously agreed to treatment observation.

## Exclusion criteria

1) Patients who are eligible for DOT but not suitable for VOT due to:

- a) Need for injectable treatment regime
- b) No access to the facilities to charge a smart phone.

2) Patients in whom the primary outcome cannot be measured because they have less than 2 months of treatment remaining.

3) MDRTB patients requiring twice daily treatment who will be recruited into a non-randomised arm of the study where VOT is offered, with the same follow up as the other study arms. This represents small numbers of patients and is planned because DOT is highly difficult to organise in this group and VOT is therefore already considered the optimal arrangement. Also due to the small number of MDRTB patients, it would be difficult to randomly assign participants to these treatment groups.

### **11a) Interventions for each group**

VOT: Daily submission of VOT clip using dedicated smartphone with pre-loaded app allowing upload to a secure server. Participants will be trained on how to lay out each drug on a labelled laminated medication sheet with a space for each drug and take each drug type individually saying either the name of the drug or the colour of the pills, size, and the number taken. Participants will be asked to show their mouth is empty by opening their mouth and sticking out their tongue and finally be asked to report any symptoms from a list of key side effects (which will be printed on the reverse of the laminated medication sheet – **Appendix 1 & 2**). Any reported or observed side effects will be addressed by study nurses as indicated in **Appendix 3**.

Training will include submission of test videos.

VOT clips will be submitted automatically as soon as the phone is connected to a cellular data network (data plan provided with phone) or wireless network.

VOT clips will be read by a study nurse/VOT observer daily during weekdays with weekend clips read on Mondays.

No incentives or travel costs will be provided but participants will be able to make use of study smartphone for e-mails, domestic telephone calls and internet searches (limited data downloads apply).

After any missed dose of VOT the observer will attempt to contact the patient by telephone to find out what the problem is and encourage submission of further video clips. If this is a technical problem that cannot be resolved over the phone a visit will be arranged to resolve this. If they are unable to contact them within 24 hours of a missed dose they will contact the case manager to discuss.

DOT: A trained health professional, or responsible lay person supported by a trained health professional, provides the prescribed medication and observes the patient swallowing every tablet prescribed (or for some schedules observing doses during weekdays with self-administered therapy at weekends). Organised by clinic according to usual practice – may be

- a) clinic based
- b) community based working with a responsible professional such as a hostel worker or pharmacist
- c) through a DOT worker outreaching DOT.

Clinics may choose to use incentives and provide travel costs as per normal practice

After each missed dose of DOT the case manager will attempt to contact the patient by telephone to find out what the problem is and encourage re-engagement.

For patients who have already crossed over study arms and continue to be non-adherent the clinic responsible for their care will determine the preferred mode of continuing to support adherence for the remainder of their care.

**11c) Strategies to improve adherence to intervention protocols, and any procedures for monitoring adherence (e.g, drug tablet return, laboratory tests)**

Participants will receive training in how to submit VOT clips during a household or clinic visit (according to participant preference) with additional training provided if participants fail to return clips or send unsatisfactory clips.

Adherence is primary outcome – see section 12.

**11d) Relevant concomitant care and interventions that are permitted or prohibited during the trial.**

In the DOT arm clinics may use incentives and enablers (mainly travel expenses) as per usual practice.

VOT arm patients are able to make use of study smartphone for e-mails, domestic telephone calls and internet searches (limited data downloads apply). However on enrolment they will be asked to sign a form (Mobile Phone Sign Out Form – Appendix 4) agreeing to the appropriate use of the mobile phone and the understanding that they may be returned to the DOT arm if the phone is lost or stolen. A copy will be retained by the study and the participant. Similarly, a release form (Mobile Phone Return Form – Appendix 5) will be completed and a copy given to the patient when the patient returns the phone to a team member.

When phones are returned to the study team they will be thoroughly cleaned with Sani-Cloth CHG 2% wipes. All areas of the phone will be wiped and made damp with the cloth. The phone will then be left on a clean paper towel until dry. Once dry it can be stored in the usual manner.

Dosset boxes are allowed in either arm.

VOT arm participants living outside of mobile phone signal coverage areas will receive help in identifying a local wireless network they can log onto.

VOT observers may contact participant via email, text or telephone to encourage them to continue to submit videos.

Patients in VOT or DOT arms may be referred to relevant agencies to address social /addiction issues. The responsibility for this referral rests with the treating clinic.

## 12) Outcomes

### *Primary Outcome Measure:*

Proportion of participants having more than 80% of scheduled VOT/DOT sessions successfully completed in the 2 months following randomisation (binary aggregation) in participants with a minimum of 6 weeks follow up data.

### *Secondary Outcome measures:*

#### *Collected continuously:*

- Proportion of doses observed over 2 months (continuous variable – comparison of means)
- Proportion of doses observed over 6 months (continuous variable – comparison of means)
- Reported side effects

#### *Collected directly by study at baseline and through telephone interview of participant at 2 and 6 months:*

- Quality of Life (EQ5D)
- Participant satisfaction (Likert scale)
- Participant resource use for DOT/VOT (Participant time, missed work)
- Employment
- Hospitalisation

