Day zero. Time 0-5 mins – Clinic nurse discusses the recommendation that the patient be treated with DOT and the possibility of being involved in a study of how best to observe treatment (face to face) or using video observed therapy. (A, B, C)

Day zero – Time 5-25 minutes - Clinic nurse provides patient information sheet to patient and allows them to assess whether they wish to receive further information. (A, B, C)

Day zero – Time 25-50 minutes –Clinic nurse (A) or study nurse (B or C) explain the study, seek written consent, randomise and arrange onward care.

Day zero – Time 50-60 minutes - study nurse (A) or clinic nurse (B, C) collect baseline data largely populated from existing clinical data/care records.

Day zero Time 60 minutes -120 minutes (A & B) – Training in use of VOT and provision of smart phone.

Day one (or first working day after day zero) – (C) VOT training up to 1 hour at patients home or at clinic depending on patient preference.

Day one (A & B) or two (C) – VOT arm – patient attempt to submit VOT clip unaided, study team liaises and arranges further training if necessary.

Day one (or first scheduled DOT appointment) – patient begins attending for DOT.

[figure not shown]
0-2 months – regular DOT/VOT with adherence data collection and monitoring of side effects.

2 months – Study team contact participant by telephone to complete follow up questionnaire covering satisfaction with DOT or VOT, Time spent on DOT or VOT, Employment and quality of life, periods of time spent away from home.

Regular out-patient appointment closest to 2 months clinic nurse requests sputum sample to test for culture conversion at local laboratory.

6 months or end of treatment - Study team contact participant by telephone to complete end of follow up questionnaire covering satisfaction with DOT or VOT, Time spent on DOT or VOT, Employment and quality of life, periods of time spent away from home. For patients still requiring onward care the study will liaise with the clinic and Find&Treat to organise continuing DOT or VOT.

Schematic of participant timeline

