## **Methods: Data collection, management, and analysis**

### **18a) Data collection methods**

Recruitment data (CRF 1 - Appendix 7): Recruiting clinics will collect anonymous data on the characteristics of patients who were approached for the trial but declined to participate using a study recruitment log sheet. This will include age, sex and factors that make them eligible for DOT.

Baseline Data (CRF 2 – Appendix 8): Study or clinic nurses will collect baseline data at the time of initial recruitment. This mainly consists of data already routinely collected by clinics, covering patient demographics, disease categorisation and factors that make them eligible for DOT. It will also include the validated EQ-5D quality of life scale and information on employment status and approximate weekly salary

VOT/DOT diary (CRF 3 – Appendix 9):

This will be recorded by the DOT observer at the time of the scheduled session and by the VOT observer at the time of reading scheduled video clips. DOT/VOT observers will be trained to complete (CRF 3 – see section 18a) consistently. CRF3 will be faxed/emailed on a weekly basis to the study centre with the study centre following up with DOT observers when weekly forms are not returned. CRF3 will be completed directly at the study centre on the VOT reading system.

The VOT reading system includes: fields to identify when doses are scheduled; when clips are submitted and read and the following categorisation of clips:

Patient took meds?

- Y (Yes, all meds)
- P (Probably)
- S (Yes, some meds)
- N (No meds taken)
- U (Unable to tell)
- DNA / Did not send clip

This data will be used for the primary outcome and secondary adherence outcome measures.

The system also collects additional data on video and audio quality. The system collects data on geo-location at the time of recording. This will be collected if the participant provides separate consent for this.

DOT: A DOT diary will be completed by DOT observers showing when doses are scheduled to be observed, whether or not the participant attended, when they attended and whether they took the medicines categorised as above.

Patient 2 and 6 month follow up (CRF 4a & 4b – Appendix 10): The study team will contact the participant by telephone to complete a 5 minute questionnaire covering

- Quality of Life (EQ5D)
- Participant satisfaction (Likert scale)
- Participant resource use for DOT/VOT (Participant time, missed work)
- Employment
- Hospitalisation

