## **Statistical methods**

### **20a) Statistical methods for analysing primary and secondary outcomes.**

Characteristics of those randomised and those not randomised due to refusal or exclusion criteria will be compared. Baseline characteristics of those randomised to intervention and control arms will be compared to check for balanced randomisation. An intention to treat analyses will be used. Categorical outcomes will be compared across groups using the chi-square test or Fisher's exact test as appropriate. Continuous variables will be compared across groups using the Wilcoxon rank-sum test.

For some DOT schedules weekend doses are planned to be self-observed due to difficulty in providing DOT at the weekend. For the primary outcome these doses will not be considered in the denominator of scheduled doses, however, as this is a valuable advantage of VOT, secondary analyses will include these weekend doses as part of the treatment schedule). When participants are in hospital their dose will be considered to have been observed. When participants are in prison or custody the dose will be considered to have been observed if it can be verified with offender health that they were aware of the treatment regime. When patients are out of the country VOT participants will be encouraged to continue to take VOT clips which can either be submitted via a wifi connection or will automatically submit on return to the UK. Doses due during time abroad will not be considered as part of the primary outcome for either arm, but will be included in the secondary analyses to explore the potential value.

Patients who cross-over trial arms (see section 11b) prior to the end of 2 month follow up will be considered a failure for the primary outcome.

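### Five secondary outcomes are collected at 2 and 6 months only by telephone, yet entry needs no phone and only the VOT arm is lent one, so the chance of being reached can depend on allocation

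*Protocol*

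**What the plan says.** **Mode of collection.** Section 12 lists five items (EQ-5D, satisfaction, participant resource use, employment, hospitalisation) as collected at baseline and then "through telephone interview of participant at 2 and 6 months". The timeline in section 13 gives the same mode: "Study team contact participant by telephone to complete follow up questionnaire". Section 18a says the study team will "contact the participant by telephone to complete a 5 minute questionnaire covering" these five items. None of the three sections names a clinic, face-to-face, proxy or record-based alternative.

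**Entry.** Section 10 admits "Any patient 16 years of age or older eligible for DOT at participating clinics". The only exclusion that concerns a phone is "No access to the facilities to charge a smart phone", which is about charging a device and not about having one.

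**What each arm receives.** Under section 11a the VOT arm gets a study smartphone, and "participants will be able to make use of study smartphone for e-mails, domestic telephone calls and internet searches". Section 11d adds that the phone is signed out and later returned, and that a participant whose phone is lost or stolen may go to the DOT arm. For DOT, sections 11a and 11d allow incentives and travel costs; no phone is supplied.

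**Other sources.** Section 18b uses national surveillance for the final treatment outcome, and clinic attendance and medication collection for DOT participants stepped down to self-administration. Section 20a states "When participants are in hospital their dose will be considered to have been observed" but does not say where hospital status comes from. Section 20c describes, in general terms, a sensitivity analysis of the missing-data assumption followed by multiple imputation.

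**The concern.** The device needed to obtain the outcome is part of one of the two interventions. A participant without a phone who is allocated to VOT acquires a number the study team can call; the same participant allocated to DOT does not. Non-response can then differ by arm because of allocation, in a population that section 6 describes as including homelessness, imprisonment and drug or alcohol use. Some participants without a working phone are foreseeable.

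At stake is the randomised comparison of these five outcomes, for which section 20a specifies intention to treat, and the part of the cost-effectiveness objective that draws on quality of life and participant resource use. If people without a phone are in worse health, they are under-represented among DOT respondents, and VOT looks worse than it is. Reachability may also change within the VOT arm, because a participant who returns or loses the phone loses that route of contact.

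**Working it through.** **1. The premises side by side**

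| Element | VOT | DOT | Section |
|---|---|---|---|
| Own phone needed for entry | No | No | 10, exclusion criteria |
| Phone supplied | Yes, usable for calls | No | 11a, 11d |
| Route for the five outcomes | Telephone only | Telephone only | 12, 13, 18a |
| Written fallback | None | None | 12, 13, 18a, 18b |

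That people without a phone are eligible is inferred from the absence of a criterion; the protocol does not say so outright.

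**2. Number per arm**

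The protocol gives no figure for response or phone ownership, so the only figure of its own to reproduce is the sample size. For 60% v 75%, 90% power and two-sided 5%, with unpooled variance:

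n = (1.960 + 1.282)² × (0.60×0.40 + 0.75×0.25) / 0.15² = 10.51 × 0.4275 / 0.0225 ≈ 200 per arm, as in section 14.

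**3. Assumptions, none of them in the protocol**

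- no true difference between arms;
- a share w without their own phone: 5%, 10%, 20% or 30%;
- 85% response among those who can be reached;
- mean EQ-5D 0.60 without a phone and 0.75 with one;
- hospitalisation 25% without a phone and 10% with one;
- in VOT, those without their own phone respond like everyone else; in DOT, none of them responds.

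**4. Formulae**

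Expected respondents: VOT 200 × 0.85 = 170; DOT 200 × 0.85 × (1 − w).

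EQ-5D: the VOT respondent mean is 0.75 − 0.15w and the DOT respondent mean is 0.75, so the difference (VOT − DOT) is −0.15w.

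Hospitalisation: the VOT respondent risk is 0.10 + 0.15w and the DOT respondent risk is 0.10, so the difference is +0.15w.

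The 85% cancels out of both differences.

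| w | VOT respondents | DOT respondents | EQ-5D difference | Hospitalisation difference |
|---|---|---|---|---|
| 5% | 170 | 161.5 | −0.0075 | +0.75 points |
| 10% | 170 | 153 | −0.015 | +1.5 points |
| 20% | 170 | 136 | −0.030 | +3.0 points |
| 30% | 170 | 119 | −0.045 | +4.5 points |

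**5. Why these are upper bounds for the assumed gaps**

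Let DOT participants without a phone respond at a fraction f of the rate of the others. Their share among DOT respondents is wf / (1 − w + wf), and the EQ-5D difference is −0.15 × [w − wf / (1 − w + wf)]. At f = 0 this is −0.15w, as tabulated. At f = 1 it is zero. It is also zero at w = 0.

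The differences scale with the assumed gap. With hospitalisation of 20% or 30% instead of 25% in those without a phone, the difference is 1 to 2 points at w = 10% and 3 to 6 points at w = 30%.

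**6. Effect on a test**

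Take an assumed EQ-5D SD of 0.25 and a normal test of means. At w = 20% the standard error is 0.25 × √(1/170 + 1/136) = 0.0288, the standardised shift is 0.030 / 0.0288 = 1.04, and the two-sided 5% test rejects in 18.1% of trials. The same steps give 5.9%, 8.4% and 32.5% at w = 5%, 10% and 30%. These too assume f = 0. Section 20a plans a Wilcoxon test, so they indicate scale only.

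**The case against.** The case against is substantial.

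- **DOT participants are seen in person.** Section 6 describes at least three visits a week, section 18a has DOT observers reporting weekly, and section 18b relies on regular contact. Staff could relay a call, and section 11a already presumes that a DOT participant can be telephoned after a missed dose. This makes complete non-response unlikely and the table an upper bound. It does not close the gap, because no section asks anyone to arrange such a call for the study interview.
- **Crossover blurs the contrast.** DOT participants who switch to VOT gain a phone, and VOT participants who lose theirs may go to DOT. The model ignores both.
- **The inputs are assumed.** They are: the share without a phone, the EQ-5D and hospitalisation gaps, the SD and the response rate. The true bias could be nil.
- **A fallback has its own bias.** It would be used mainly in DOT, so mode of completion would follow arm, and rating satisfaction with DOT in front of the DOT observer invites favourable answers. This stands and shapes the fix.

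A reader might also infer four stronger claims that the protocol does not support:

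- *All follow-up is affected.* Observed doses, observer questionnaires, sputum culture and surveillance outcomes have other sources.
- *A participant without a phone cannot be interviewed at all under DOT.* The face-to-face contacts make it possible, only harder.
- *Hospitalisation is lost in those who had it.* Discharged patients can report an earlier stay; those who have died or cannot be reached cannot.
- *Multiple imputation cannot help.* Section 18a collects EQ-5D and employment at baseline, which could inform it, although the assumption about unreached DOT participants would remain untestable.

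**Conclusion.** The point holds for five secondary outcomes and not for the primary outcome. As written, sections 12, 13 and 18a make a telephone the only route to these outcomes, entry does not require one, and one arm supplies it. Participants without their own phone are therefore easier to reach if allocated to VOT, and neither section 18b nor section 20c deals with that difference.

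The size cannot be settled from the protocol. It ranges from zero, if all own a phone or all are reached by other means, to the upper bounds in the working: about 0.015 to 0.045 on EQ-5D and 1.5 to 4.5 points on hospitalisation for a 10% to 30% share, and half the 10% values for a 5% share. The direction, VOT appearing worse, rests on the assumption that people without a phone are in poorer health. The mode of collection is fixed in the protocol itself, so the remedy belongs there.

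**What to change.** Amend sections 12, 13 and 18a as follows.

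1. Keep the telephone call as the first attempt in both arms, with a stated window.
2. For anyone not reached in that window, in either arm, have the same 5-minute CRF 4 self-completed at the clinic appointment nearest 2 months after randomisation, which section 18a already uses for the sputum sample. At the later time point, use an existing clinic appointment near 6 months or the end of treatment. The DOT or VOT observer should not be present.
3. Take hospitalisation (yes/no and dates) from the treating clinic for every randomised participant in both arms. Hospital days must be known anyway to apply the dose-counting rule in section 20a.
4. Record access to a phone at baseline on CRF 2 and mode of completion on CRF 4, and report response by arm.

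The cost is protocol and CRF wording and a small amount of clinic time for participants not reached by telephone. The drawback is a mixed mode of completion that may be unbalanced between arms; a sensitivity analysis restricted to telephone responses should examine it.
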